S-GAIS	Subject Global Aesthetic Improvement Scale
S-GSQ	Subject Global Satisfaction Questionnaire
TM	Trademark
MeDRA	Medical Dictionary for Regulatory Activities

1. ETHICS

1.1. Institutional Review Board (IRB)/Independent Ethics Committee (IEC)

It is the responsibility of the investigator to have prospective approval of the study protocol, protocol amendments, informed consent forms, and other relevant documents, e.g., recruitment materials, if applicable, from the IRB/IEC. All correspondence with the IRB/IEC should be retained in the Investigator File (Site Master File). Copies of IRB/IEC approvals should be forwarded to the Sponsor.

The only circumstance in which a protocol amendment may be initiated prior to IRB/IEC approval is where the change is necessary to eliminate apparent immediate hazards to the subjects. In that event, the investigator must notify the IRB/IEC and the Sponsor in writing within 5 working days after the implementation.

1.2. Ethical Conduct of the Study

The study will be performed in accordance with the protocol, International Conference on Harmonization Good Clinical Practice guidelines (ICH E6) and applicable local regulatory requirements and laws.

1.3. Subject Information and Consent

All parties will ensure protection of subject personal data and will not include subject names on any forms, reports, publications, or in any other disclosures. In case of data transfer, Sponsor will maintain high standards of confidentiality and protection of subject personal data.

The informed consent form must be agreed to by the Sponsor and the IRB/IEC and must be in compliance with ICH GCP, local regulatory requirements, and legal requirements.

The investigator must ensure that each study subject, or his/her legally acceptable representative, is fully informed about the nature and objectives of the study and possible risks associated with participation. The investigator, or a person designated by the investigator, will obtain written informed consent from each subject or the subject's legally acceptable representative before any study-specific activity is performed. The informed consent form used in this study, and any changes made during the course of the study, must be prospectively approved by both the IRB/IEC and the Sponsor before use. The investigator will retain the original of each subject's signed consent form.

Investigational Device: ThermiRF

Protocol No.: Thermi_0005

Version Date: Final 10-May-2016

2. INVESTIGATORS AND STUDY ADMINISTRATIVE STRUCTURE

Details on the administrative structure of the study (e.g., investigator, coordinating, steering committee, administration, monitoring and evaluation committees, institutions, statistician, central laboratory facilities, external service provider (ESP or CRO), or clinical study supply management) will be maintained in the Sponsor's Study Master File throughout the study for inclusion in the clinical study report.

Investigational Device: ThermiRF

Protocol No.: Thermi_0005

Version Date: Final 10-May-2016

3. INTRODUCTION

3.1. Background and Rationale

Biochemical changes in dermal connective tissue lies at the foundation of skin laxity, often leading to the inevitable “Aging Face Syndrome.” The appearance of a young and well defined neck is deemed to have cervicomental angle of 90 ° – 105 °, a good tone, a well-defined mandibular border, no accumulation of fat in the submental area, and no evidence of platysma bands [1].

In the course of aging, the neck serves as an indicator for the loss of collagen and elastin causing excessive skin laxity, an increase in submental fat and loose jowls along the mandibular border. A 2014 American Society for Dermatologic Surgery consumer survey found 68 percent of respondents were concerned about excess fat under the chin and neck. Data were obtained through a blind online survey conducted in April 2014 through the web-based Contribute service. The survey received 8,315 responses.

Laxity of submental area is therefore, a common cosmetic complaint of the aging population. As the “baby boomer” generation reaches later life, aesthetic surgical medical interventions are becoming increasingly sought after by patients to aid and improve the cosmetic profile of these persons.

Thermi plans to evaluate the safety and effectiveness of ThermiRFTM radiofrequency in the treatment of submental skin laxity using. The planned treatment uses targeted temperature controlled RF to achieve lifting in subjects with mild to moderate severity defined as normal muscle and mild to moderate skin laxity and mild to moderate fat on the submental area. Additionally biomechanical changes of the skin will be evaluated using the Cutomer® which may be evident as a result of the ThermiRF treatment [6].

The ThermiRF system uses radiofrequency to apply heat to target areas using electrocoagulation; this is a percutaneous minimally -invasive technique.

ThermiRF Device

The ThermiRF device is a minimally invasive radiofrequency solution, and an established therapeutic modality for the treatment of nerve tissue ablation and electrocoagulation. The use of radiofrequency in aesthetics is well published. [2-4]. the temperature controlled radiofrequency is less-invasive and provides a better safety profile (reduced risk) when compared to surgery, other more invasive treatments and non-temperature controlled energy devices. The ThermiRF device delivers a controlled thermal endpoint as a result of its proprietary software algorithm and feedback loop that consistently measures the tissue temperature at the tip of the treatment RF electrode.

[figure not shown]
As the electric current permeates a tissue layer, ions found within that layer, deliver or carry the current. This, in turn, increases the kinetic activity of the ions. Increased ion kinetics and oscillations engenders resistive tissue thermogenesis.

Thermogenesis is calculable via the Specific Absorption Rate (SAR) equation, which assesses local electrical conductivity and magnitude of local electric current density generated around the electrode (Equation 1).

$$SAR = \frac{\sigma}{\rho} |E|^2 = \frac{1}{\sigma \cdot \rho} |J|^2$$

The electric field strength generated is capable of heating tissue in close proximity to the electrode. Thermal conduction attenuates the heating of tissue as you move further from the electrode. With proper controls, generating the ideal thermal endpoint will occur very close to the electrode, thereby affecting only the intended target tissue area (Figure 1).

Figure 1: Distribution of RF-induced heat

Regulation of tissue temperature derives from power control. Power (P) is equal to the voltage multiplied by the current; the Power is delivered via the radiofrequency electrode. Depending on the tissue impedance, the power will need further adjustment, ensuring the proper voltage/current is delivered to satisfy the tissue impedance. Finally, thermal sensors – thermocouples – integrated within the radiofrequency electrode to allow for accurate measurement of tissue temperature and the system will adjust power to maintain the physician selected therapeutic temperature. With these proper controls in place, selective thermogenesis serves as a viable treatment for numerous medical conditions.

The generation of heat is enough to promote tissue necrosis within a defined area. Accordingly, percutaneous radiofrequency can be administered for destruction of terminal fibers, which in turn, contracts tissue. Overall, percutaneous radiofrequency administers energy in a highly selective manner to induce the desired clinical outcome; “lift” achieved through tissue contracture and tightening.

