4.2. Secondary Objective/Endpoint

- Overall aesthetic improvement of the submental area and jawline definition at Days 90 and 180 evaluated by the investigator and subject, using the following subjective assessment:
 - Qualitative assessment based on 2D photography performed by blinded panel
 - Physician - Global Aesthetic Improvement Scale Scores (P-GAIS)
 - Subject – Global Aesthetic Improvement Scale Scores (S-GAIS)
 - Physician - Global Satisfaction Questionnaire (P-GSQ)
 - Subject - Global Satisfaction Questionnaire (S-GSQ)

Each individual endpoint will be based on study subject population response for each individual endpoint.

- Safety will be evaluated using the following measures:

- Numerical Rating Scale (NRS) a 10-point pain scale
 - Self-reported and observed adverse event

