9.3. Assessment of Safety

Safety assessment will include an evaluation of the treatment area to assess overall quality and integrity of tissue layers for subjects that have completed treatment. All known and unknown events including known risks (see below) will be collected during the conduct of the study regardless of causality.

- Edema
- Infections
- Thermo-injury (i.e. Burns)
- Scarring
- Erythema
- Postoperative pain
- Second-degree burn treatment
- Transient paresthesia

Sensory assessment will be collected using the Numerical Rating Scale (NRS) a 10-point scale to measure pain after treatment.

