10. ADVERSE EVENT REPORTING

10.1. Introduction

All observed or volunteered adverse events regardless of treatment group or suspected causal relationship to the ID(s) will be reported as described in the following sections.

For all adverse events, the investigator must pursue and obtain information adequate both to determine the outcome of the adverse event and to assess whether it meets the criteria for classification as a serious adverse event requiring immediate notification to the sponsor or its designated representative. For all adverse events, sufficient information should be obtained by the investigator to try to determine the causality of the event. For adverse events with a suspected causal relationship to the ID, follow-up by the investigator is required until the event or its sequel resolve or stabilize at a level acceptable to the investigator, and Sponsor concurs with that assessment.

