11.2. Sample Size Determination

The sample size calculation is based on the following assumptions:

- The true response rate for subjects that do not drop out will be 70%.
- The null response rate is 45%, so a successful trial will reject the null hypothesis that the true response rate is less than or equal to 45%.
- The dropout rate will be approximately 12.5%. While some subjects that drop out may have data from Day 60 that can be carried forward in the primary effectiveness analysis, the sample size calculation assumes that none does and will therefore be treated as non-responders.
- The primary effectiveness analysis is based on a one-sided binomial proportion test that compares the null proportion to the alternative proportion.

Based on these assumptions, a minimum of 68 subjects is required to achieve 80% power at one-sided $\alpha = 0.05$, so a sample size of 70 subjects provides greater than 80% power.

Additionally based on the rule of three, sample size of at least 60 makes it possible to observe any adverse event that occurs with a frequency $> 5\%$ with 95% confidence.

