N.B.; The ThermoRF is technically identical to the Symphony RF, the marketing name of the device was changed from Symphony RF to ThermoRF. No technical modifications were made. (K130689).

1. 510(k) # 130689

Device Name: SymphonyRF Generator (ThermoRF)

Indication for use: dermatological and general surgical procedures for electrocoagulation and hemostasis; and to create lesions in nervous tissue

2. 510(k) #: K-033981

Device Name: Smith and Nephew ElectroThermal 20S Spine Generator

Indication of use: Intended to create lesions in nervous tissue, and to coagulate and decompress disc material when used in combination with Smith and Nephew thermal/coagulating probes.

3. 510(k) #: K121858

Device Name: The Acessa System

Investigational Device: ThermoRF

Protocol No.: Thermo_0005

Version Date: Final 10-May-2016

Indication of use: Percutaneous use for laparoscopic coagulation and ablation of soft tissue

4. 510(k) #: K121481

Device Name: The INFINI Radiofrequency System

Indication of use: For use in dermatologic and general surgical procedures for electrocoagulation and hemostasis, and the percutaneous treatment of facial wrinkles

5. 510(k) #: K082391

[figure not shown]
Device Name: Primaeva Medical

Indication for use: For use in dermatologic and general surgical procedures for electrocoagulation and hemostasis, and the percutaneous treatment of wrinkles

IRB approved study: The protocol was reviewed and approved by the local ethics committee (Independent Investigational Review Board, Inc, Plantation, FL, USA) Millheiser LS, Pauls RN, Herbst SJ, Chen BH. Radiofrequency treatment of vaginal laxity after vaginal delivery: non-surgical vaginal tightening. J Sex Med. 2010; 7(9):3088-95.

DEVICE LABELING

The ThermoRF is manufactured in accordance with the Good Manufacturing Procedures set forth by the FDA. Per CE (Certified European) standards and testing results and has been validated by a third party (Intertek Testing Services NA Inc. Report Reference No. 100584146BOX-004) for conformance to IEC 60601-1-2 (EMC) and IEC 60601-1 (electrical safety). Third party verification of IEC 60601-1-4 and IEC 60601-1-6 Collateral Standards was performed as well.

In addition, the device used in this clinical study shall be labeled with the following statement: NON-SIGNIFICANT RISK STATEMENTS

“CAUTION – Investigational device. Limited by United States law to Investigational use.”

Do you contend that this device as used in this protocol is an NSR device?

Yes No

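### The assessment labelled sensory is a pain scale, so painless paresthesia, a listed risk, relies on adverse events being observed or volunteered

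*Protocol*

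**What the plan says.** **The risk.** Protocol section 9.3 includes "Transient paresthesia" in its list of known risks and says that these will be collected whatever their cause. The risk list in section 7.7 does not name it.

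**The measure.** The same section 9.3 then states: "Sensory assessment will be collected using the Numerical Rating Scale (NRS) a 10-point scale to measure pain after treatment". Section 9.1 describes the NRS as unidimensional, running from no pain to the worst pain possible. Section 4.2 likewise lists it as "Numerical Rating Scale (NRS) a 10-point pain scale", beside self-reported and observed adverse events.

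**The adverse event route.** Section 10.1 covers "All observed or volunteered adverse events regardless of treatment group". Section 9.1 adds an investigator examination of the treated area and nearby anatomy, and section 9.3 an evaluation of the condition of the tissue layers. Neither specifies a sensory test. Adverse event assessment is listed at each follow-up visit in section 8, and the first of these is Day 30.

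**The analysis.** SAP section 11.1 and Table 16 summarise the NRS descriptively from Day 30 on, with no pre-treatment value. Adverse events are tabulated by system organ class and preferred term.

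**The device.** Section 3.1 calls it "an established therapeutic modality for the treatment of nerve tissue ablation and electrocoagulation", and Appendix 8 gives a cleared indication that ends with "and to create lesions in nervous tissue". On how tissue is tightened, section 3.1 says that "percutaneous radiofrequency can be administered for destruction of terminal fibers, which in turn, contracts tissue".

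**The safety sample size.** Section 11.2 says that a "sample size of at least 60 makes it possible to observe any adverse event that occurs with a frequency" above 5%, with 95% confidence.

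**The concern.** The protocol names a sensory harm and announces a sensory assessment, but the instrument it assigns can record only pain. A subject whose treated area is numb or tingling without pain gives the lowest score. In Table 16 that subject cannot be told apart from one with normal sensation.

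Erythema, edema and burns can be seen on examination. Altered sensation usually cannot, so its recording depends on the subject raising it. A transient symptom may also have resolved before the Day 30 visit, in which case the subject would have to recall it. At stake is the count of one listed risk in a study that has safety among its aims, and how far the detection statement in section 11.2 can be relied on for that risk.

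**Working it through.** **Step 1. Is sensation asked about anywhere else?**

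| Place | What it captures | Painless numbness or tingling |
|---|---|---|
| NRS (Protocol 9.1, 9.3; SAP 11.1, Table 16) | Pain intensity | Scores no pain |
| Investigator examination (Protocol 9.1) | What the investigator notes; no sensory test stated | Only if raised or elicited |
| Tissue evaluation (Protocol 9.3) | Condition of tissue layers | Not addressed |
| Adverse events (Protocol 10.1; SAP 11.2) | Observed or volunteered events | Captured if mentioned |
| Visit lists (Protocol 8.3 to 8.5), Appendix 1, SAP shells | NRS, adverse events, photographs, questionnaires, elasticity | No item |

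The satisfaction questionnaires (Appendices 4 and 5) ask how the skin feels, but the options are tightness, firmness, smoothness, easier make-up or shaving, and no change.

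**Step 2. Reproduce the section 11.2 statement.** The inputs are n = 60 and a true frequency f = 5%.

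- Chance of no case: (1 − 0.05)^60 = 0.046, so the chance of at least one is 95.4%.
- Exact 95% upper bound with 0 of 60 events: 1 − 0.05^(1/60) = 4.87%. The rule of three gives 3/60 = 5.0%.

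The statement reproduces. It treats every event that occurs as recorded.

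**Step 3. Relax that condition.** Let s be the share of affected subjects whose event is recorded. The documents give no value for s, so a range is assumed. The chance of recording no case is (1 − f·s)^n. The 5% frequency comes from section 11.2; it is not an estimate of the paresthesia rate.

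| s (assumed) | f·s | n = 60 | n = 70 |
|---|---|---|---|
| 1 | 0.0500 | 0.95^60 = 4.6% | 0.95^70 = 2.8% |
| 3/4 | 0.0375 | 0.9625^60 = 10.1% | 0.9625^70 = 6.9% |
| 1/2 | 0.0250 | 0.975^60 = 21.9% | 0.975^70 = 17.0% |
| 1/3 | 0.0167 | 0.9833^60 = 36.5% | 0.9833^70 = 30.8% |

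**Step 4. The same result as a detectable frequency.** With n = 60, the smallest true frequency that gives 95% confidence of at least one recorded case is 4.87%/s: 4.9% at s = 1, 6.5% at 3/4, 9.7% at 1/2 and 14.6% at 1/3.

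**Step 5. Day 60.** Section 8.4 lists both NRS and adverse event assessment at Visit 4, and SAP section 11.1 summarises the NRS at Day 60. Appendix 1 marks neither at that visit. These places conflict.

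**The case against.** The strongest reply is that paresthesia is already within adverse event collection. It is named in section 9.3, adverse event assessment is scheduled at follow-up visits, self-reported events are a safety endpoint, and the investigator examines the area. On this view, soliciting symptoms or not is a design preference. Much of this stands, and it rules out several stronger readings.

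- A reader might infer that the NRS is the only prompted safety measure. The documents do not support that, because adverse event assessment and an examination are planned. The NRS is the only structured or scaled measure described.
- A reader might infer that nerve injury would be reported as a good result. The NRS has no success threshold and no role in effectiveness, painful nerve injury would raise it, and a painless deficit can still appear in the adverse event tables. The weakness is confined to what the NRS can show.
- A reader might take nerve destruction to be the intended mechanism here. Section 3.1 does not say that the terminal fibers are nerve, and section 6.2 describes electrocoagulation and neocollagenesis. The nerve-ablation wording in section 3.1 and Appendix 8 concerns the device's general and cleared uses.

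Two further limits apply. The CRFs, dated 18AUG2016 in SAP section 2, were not available. The evaluability checklist refers to a specific eCRF page for rash and to adverse events of special interest, so a prompt for sensory change may exist. Also, incomplete recording weakens section 11.2 for every adverse event. It matters more for a symptom that cannot be seen, but the documents do not say by how much.

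What the reply does not answer is the mismatch within section 9.3 between a listed sensory risk and a sensory assessment that cannot register it when there is no pain.

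**Conclusion.** The point holds as an ascertainment and labelling gap for one listed risk. As the protocol and SAP are written, painless sensory change is recorded only if someone raises or notices it, so it can be under-counted.

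For a 5% event in 60 subjects, the chance of seeing no case rises from 4.6% with full recording to about 10%, 22% or 36% when three quarters, one half or one third of cases are recorded. These figures illustrate the dependence on recording. They rest on assumed shares, on the same share applying to each affected subject independently, and on the 5% benchmark. They do not estimate how often paresthesia occurs or goes unreported. The conclusion also depends on the unseen CRFs carrying no sensory prompt.

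The primary effectiveness analysis is untouched. This is a cheap improvement to safety ascertainment.

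**What to change.** 1. In Protocol section 9.3, call the NRS a pain assessment. SAP section 11.1 does not use the sensory label, so its description of the NRS needs no relabelling.
2. Add to section 9.3, the visit lists in section 8 and Appendix 1 one yes/no question on numbness, tingling or weakness in the treated area. Ask it at Visit 1 as a baseline and at each existing follow-up visit. Give it a recall period (since treatment at the first follow-up, since the last visit thereafter), so that an episode that resolved before Day 30 is still captured.
3. Record each new yes as an adverse event.
4. Add to SAP section 11 a table block beside Table 16 with n/N and an exact 95% confidence interval by visit.
5. Reconcile section 8.4, Appendix 1 and SAP section 11.1 on whether NRS and adverse events are collected at Day 60.

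The cost is one CRF line at existing visits and one table block, with no added visit or procedure. The downside is that a solicited question may raise the reported adverse event rate, so the report should say that these events were solicited. If the CRFs already carry such a prompt, only the relabelling, the table block and the Day 60 reconciliation remain, plus the Visit 1 baseline and recall period if the prompt lacks them.

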3.2. Regulatory Status

The ThermoRF® Device is classified by the FDA/IEC as a Class 2 radiofrequency device. The device used in this study was cleared by the Food and Drug Administration (FDA) for dermatological and general surgical procedures for electrocoagulation and hemostasis **[K130689]**.

Investigational Device: ThermiRF

Protocol No.: Thermi_0005

Version Date: Final 10-May-2016

4. STUDY OBJECTIVES

4.1. Primary Objective/Endpoint

- Improvement in overall lift of the submental area at Day 90, as determined by:
 - Quantitative assessment based on 3D photography

4.2. Secondary Objective/Endpoint

- Overall aesthetic improvement of the submental area and jawline definition at Days 90 and 180 evaluated by the investigator and subject, using the following subjective assessment:
 - Qualitative assessment based on 2D photography performed by blinded panel
 - Physician - Global Aesthetic Improvement Scale Scores (P-GAIS)
 - Subject – Global Aesthetic Improvement Scale Scores (S-GAIS)
 - Physician - Global Satisfaction Questionnaire (P-GSQ)
 - Subject - Global Satisfaction Questionnaire (S-GSQ)

Each individual endpoint will be based on study subject population response for each individual endpoint.

- Safety will be evaluated using the following measures:

- Numerical Rating Scale (NRS) a 10-point pain scale
 - Self-reported and observed adverse event

